5.1. Number of Subjects

This study will be enrolled with 12 subjects in each cohort according to in/exclusion in Part 1, planned 3 cohorts. 9 subjects randomized to the HM15136 group will be administered IP in each cohort, 3 subjects will receive placebo. In part 2, up to 66 subjects will be enrolled. Thirty (30) subjects in cohort 4 will be randomized to HM15136 or placebo in a ratio of 15:15, 12 subjects in each of the cohorts 5-7 in a ratio of 9:3. Part 2 will only be performed, if deemed necessary, after the safety data, obtained by the 9th subject's visit on Day 29 of Cohort 3 in Part 1, have been reviewed.

An independent Data Monitoring Committee (DMC) will assess the safety and will make dosing and cohort escalation assessments and recommendations for the dose and study progress of Part 2. After the review of the safety data in Part 1, Part 2 may or may not proceed.

[Part 1]

Cohorts	Number of Subjects	Treatment
Cohort 1	N=9	HM15136 0.02 mg/kg
	N=3	Placebo
Cohort 2	N=9	HM15136 0.04 mg/kg
	N=3	Placebo
Cohort 3*	N=9	HM15136 ≤0.08 mg/kg
	N=3	Placebo

* Dosage of Cohort3 can be adjusted, but cannot be over the dosage presented in the table.

The escalated dose should not be over twice the dose of the previous cohort.

[Part 2]

Cohorts	Number of Subjects	Treatment
Cohort 4* (DM)	N=15	HM15136 0.06 mg/kg
	N=15	Placebo
Cohort 5 (DM)	N=9	HM15136 ≤0.02-mg/kg
	N=3	Placebo
Cohort 6** (DM)	N=9	HM15136 ≤0.04-mg/kg
	N=3	Placebo
Cohort 7** (DM)	N=9	HM15136 ≤0.06-mg/kg
	N=3	Placebo

* In part 2, enrolling 30 subjects per cohort 4, 15 subjects randomized to HM15136 group will be administered IP, (15 subjects will receive placebo).

The dose and study progress of Part 2 should be guided by the recommendation of the DMC. After the review of the safety data in Part 1, Part 2 may not proceed.

** Cohorts 6 and 7 will be optional.

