The DMC will assess the safety and will make dosing and cohort escalation assessments and recommendations for the progress of Part 2. After the review of the safety data in Part 1, Part 2 may or may not proceed.

Cohort 4 may be conducted with a lower number of subjects to adopt escalation design as previously performed in Part 1 for the safety assessment of the T2DM subjects.

The maximum dose level for Part 2 will not exceed 0.06 mg/kg (tentative dose for Cohort 5 may be 0.02 mg/kg, tentative dose may be 0.04 mg/kg for Cohort 6). This dose level has been previously approved for subjects with T2DM by the independent DMC. Therefore, the decision to proceed to the next cohort/dose level from cohorts 5-7 will be made per review of safety data by Sponsor, Investigator and Medical Monitor during a Data Review Meeting (DRM), which will take place after the 9th subject has completed Visit Day 43 (which is after 6 weeks of dosing).

Per DRM of Cohort 5 (after the 9th subject's visit on day 43 of Cohorts 5), a dose escalation to Cohort 6 will not proceed at this timepoint and another DRM will be held after all 12 subjects in Cohort 5 have completed the final study visit on Day 113 (=F/U Visit), to assess the safety data and to make a decision to escalate to Cohort 6 or not.

Dose escalation from cohort 6 to the subsequent cohort 7 will follow the same dose escalation scheme and DRM(s) of the previous cohort.

Cohorts 6 and Cohort 7 may be conducted at doses of 0.04 mg/kg and at 0.06 mg/kg respectively upon approval by the Investigator, Medical Monitor, and the Sponsor, if the safety is demonstrated in Cohort 5.

If sufficient safety data are collected after cohort 5 or cohort 6 have been completed, no additional cohorts will be conducted, and sponsor may choose to complete study.

The conduct of cohorts 6 and 7 is optional.

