7.3. Dose Escalation and Study Stopping Criteria

<Dose Escalation Stopping Criteria>

The procedure for determining the dose is as follows

- The main criterion for determining tolerability is emesis/vomiting (=gastrointestinal tolerability).
- Vomiting is associated with the pharmacologic administration of GLP-1 agonists and glucagon, and the severity of vomiting in this study is defined as.:
 - Moderate: 3-5 times vomiting within 24 hours (when the vomiting interval is at a minimum of 5 minutes or more, each vomiting event is counted.)
 - Severe: 6 times or more within 24 hours or requiring fluid injection via IV (intravenous) (when the vomiting interval is at a minimum of 5 minutes or more, each vomiting event is counted.)

If one of the following criteria is met, an independent DMC will meet to assess safety in real-time and make dosing and cohort escalation assessments and recommendations, such as: IP administration and dose elevation should be stopped, or the dose level should be discontinued, suspended, or a dose modification or repetition should occur prior to proceeding to subsequent dosing, or dosing can continue. All decisions to increase the dose or discontinue dosing will be decided by the DMC. The DMC will determine when the safety and/or tolerance limits have been reached.

- 1) Moderate or severe emesis occurred in 50% or more subjects in one cohort.
- 2) Severe emesis occurred in 25% or more subjects in one cohort.
- 3) At any time, if one subject dies (CTCAE grade 5 toxicity may be used as a grading scale) in one cohort.
- 4) If severe AEs (CTCAE grade ≥ 3 may be used as a grading scale) occurred in 2 subjects within one cohort.
- 5) If moderate AEs (CTCAE grade ≥ 2 may be used as a grading scale) occurred in 2 subjects within one cohort and persisted for 7 days or more.
- 6) If a SAE occurred in 1 subject or more within one cohort.
- 7) If clinically significant similar laboratory abnormalities, clinically significant ECG or V/S abnormalities, or severe AEs in the same SOC (System organ class) occurred in 2 subjects or more receiving IP representing dose limiting toxicity (DLT).

As the DMC is unblinded, any potential stopping rule event occurring in subjects receiving placebo would not be considered to be meet the stopping rule. Additionally, AEs considered to be unrelated to HM15136 would not be considered to meet the stopping rules.

< Data Monitoring Committee (DMC) >

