The DMC is a specific committee for the study and will function for safety review and dose escalation decisions as described above. The operations of the DMC will be defined in the DMC charter.

The DMC will review safety data (adverse events, clinical laboratory, vital signs and electrocardiograms, and other unblinded relevant data). There will be 3 dose decisions. In addition the DMC will have unplanned meetings should stopping criteria appear to have been met.

After Cohort 1 randomization is completed, the DMC will assess the safety and will make dosing and cohort escalation assessments and recommendations to decide whether subjects can be randomized into Cohort 2.

Dose escalation from cohort 2 to next dose level for the subsequent Cohort 3 will be based on the safety, tolerability, available PD, and available PK data obtained from cohort 1 and through the 9th subject's visit on Day 29 in cohort 2. The DMC will make recommendations for the decision whether subjects can be randomized into Cohorts 3.

The next dose level for the subsequent cohort (Cohorts 4 in Part 2) will be based on the safety, tolerability, available PD, and available PK data obtained from cohort 1, 2 and through the 9th subject's visit on Day 29 in cohort 3. An independent Data Monitoring Committee (DMC) will assess the safety and will make dosing and cohort escalation assessments and recommendations.

< Data Review Meeting >

A data review meeting will be held by sponsor, investigator and medical monitor to review safety data after the 9th subject of cohort 5 and 6 in Part 2 has completed their Day 43 visit. This time point is situated 6 weeks after the first dosing. safety data review will guide the decision for dosing and cohort escalation recommendations.. Additionally, a second DRM will be held and safety data from the 12th subject's final visit on Day 113 (=F/U Visit) will be reviewed to dose escalate.

Dose escalation from cohort 6 to the subsequent cohort 7 will follow the same dose escalation scheme and DRM(s) of the previous cohort.

Cohorts 6 and Cohort 7 may be conducted at doses of 0.04 mg/kg and at 0.06 mg/kg respectively upon approval by the Investigator, Medical Monitor, and the Sponsor, if the safety is demonstrated in Cohort 5.

If sufficient safety data are collected after cohort 5 or cohort 6 have been completed, no additional cohorts will be conducted, and sponsor may choose to complete study.

< Study Stopping Criteria >

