2.4. Dose Escalation Stopping Criteria

The procedure for determining the dose is as follows

- The main criteria for determining tolerability is emesis/vomiting (=gastrointestinal tolerability).
- Vomiting is associated with the pharmacologic administration of GLP-1 agonists and glucagon, and the severity of vomiting in this study is defined as:
 - Moderate: 3 -5 times vomiting within 24 hours (when vomiting interval is at a minimum 5 minutes or more, each vomiting event is counted.)
 - Severe: 6 times or more within 24 hours or requiring fluid injection via IV (intravenous) (when the vomiting interval is at a minimum 5 minutes or more, each vomiting event is counted.)

If one of the following criteria is met, an independent DMC will meet to assess safety in real-time and make dosing and cohort escalation assessments and recommendations, such as: IP administration and dose elevation should be stopped, or the dose level should be discontinued, suspended, or a dose modification or repetition should occur prior to proceeding to subsequent dosing, or dosing can continue. All decisions to increase the dose or discontinue dosing will be

decided by the DMC. The DMC will determine when the safety and/or tolerance limits have been reached.

- 1) Moderate or severe emesis occurred in 50% or more subjects in one cohort.
- 2) Severe emesis occurred in 25% or more subjects in one cohort.
- 3) At any time, if the subject dies (CTCAE grade 5 toxicity may be used as a grading scale) in one cohort.
- 4) If severe AEs (CTCAE grade ≥ 3 may be used as a grading scale) occurred in 2 subjects within one cohort.
- 5) If moderate AEs (CTCAE grade ≥ 2 may be used as a grading scale) occurred in 2 subjects within the one cohort for 7 days or more.
- 6) If a SAE occurred in 1 subject or more within the one cohort.
- 7) If clinically significant similar laboratory abnormalities, clinically significant ECGs or V/S abnormalities, or severe AEs in the same SOC (System organ class) occurred in 2 subjects or more receiving IP representing dose limiting toxicity (DLT).

As the DMC is unblinded, any potential stopping rule event occurring in subjects receiving placebo would not be considered as meeting the stopping rule. Additionally, AEs considered to be unrelated to HM15136 would not be considered as meeting the stopping rules.

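### The emesis stopping criteria keep placebo subjects in the denominator but drop their events, so a balanced Cohort 4 would need every HM15136 subject to be affected

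*Protocol*

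**What the plan says.** Protocol 7.3 names vomiting as the main measure of tolerability and lists seven criteria that bring the independent DMC together. Criterion 1 is "Moderate or severe emesis occurred in 50% or more subjects in one cohort". Criterion 2, in the SAP's words, is "Severe emesis occurred in 25% or more subjects in one cohort". Criterion 5, for moderate adverse events, applies only if they "occurred in 2 subjects within one cohort and persisted for 7 days or more".

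Both documents then discount placebo events. Protocol 7.3 says "any potential stopping rule event occurring in subjects receiving placebo would not be considered to be meet the stopping rule", and SAP 2.4 says "any potential stopping rule event occurring in subjects receiving placebo would not be considered as meeting the stopping rule". Events judged unrelated to HM15136 are also set aside. On unplanned meetings, Protocol 7.3 says "In addition the DMC will have unplanned meetings should stopping criteria appear to have been met".

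Cohorts are counted with their placebo subjects throughout. Cohorts 1–3 and 5–7 have 12 subjects each (9 HM15136, 3 placebo). For Cohort 4, Protocol 5.1 says "Thirty (30) subjects in cohort 4 will be randomized to HM15136 or placebo in a ratio of 15:15". Protocol 6.2 adds that "Cohort 4 may be conducted with a lower number of subjects to adopt escalation design as previously performed in Part 1".

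**The concern.** The numerator is limited to HM15136 subjects, while the denominator, on its plain reading, is the whole cohort. The share of active subjects who must be affected then depends on how many placebo subjects happen to be enrolled, which has nothing to do with tolerability.

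The clearest illustration is the 0.06 mg/kg dose. Cohort 4 gives it to subjects with T2DM at 1:1, and Cohort 7 may give up to the same dose to the same population at 3:1. If Cohort 7 runs at 0.06 mg/kg, one dose in one population faces two quite different bars.

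At stake is whether the DMC is called when moderate vomiting is common on active drug. Moderate emesis that clears in under 7 days does not meet criterion 5, so criterion 1 is the only numeric trigger for it.

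**Working it through.** **Inputs.** The thresholds are 50% and 25% (Protocol 7.3, SAP 2.4). The cohort sizes are 9 + 3 = 12 and 15 + 15 = 30 (Protocol 5.1, SAP 2.2). The plan gives no counts, trigger probabilities or emesis rates, so there is no stated figure to reproduce. Every rate below is an assumption.

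**Step 1: thresholds as written.** The number of HM15136 subjects needed is the percentage times cohort size, rounded up.

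| Criterion | 9:3 cohort | Cohort 4 (15:15) |
|---|---|---|
| 1 | 0.50 × 12 = 6, so 6/9 = 67% | 0.50 × 30 = 15, so 15/15 = 100% |
| 2 | 0.25 × 12 = 3, so 3/9 = 33% | 0.25 × 30 = 7.5, rounded up to 8, so 8/15 = 53% |

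For any balanced cohort of 2m subjects, 50% is m, which is every active subject. A smaller Cohort 4 therefore still needs 100% if it stays balanced. If it closed at 7:5, criterion 1 would need 6/7 = 86%.

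**Step 2: thresholds with HM15136 subjects as the denominator.** Criterion 1: 0.50 × 9 = 4.5, rounded up to 5 (56%), and 0.50 × 15 = 7.5, rounded up to 8 (53%). Criterion 2: 0.25 × 9 = 2.25, rounded up to 3 (33%), and 0.25 × 15 = 3.75, rounded up to 4 (27%). The two designs now nearly agree.

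**Step 3: probability that criterion 1 is met.** These are exact binomial tails. For the count across arms, the total is the sum of independent binomials for the active and placebo arms.

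| Rule | True rate on HM15136: 50% | 70% | 90% |
|---|---|---|---|
| As written, 6 of 9 | 0.25 | 0.73 | 0.99 |
| As written, 15 of 15 | 0.00003 | 0.005 | 0.21 |
| All arms, 6 of 12, placebo 10% | 0.33 | 0.78 | 0.99 |
| All arms, 15 of 30, placebo 10% | 0.008 | 0.12 | 0.62 |
| All arms, 15 of 30, placebo 20% | 0.055 | 0.33 | 0.85 |
| Active only, 5 of 9 | 0.50 | 0.90 | >0.99 |
| Active only, 8 of 15 | 0.50 | 0.95 | >0.99 |

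For example, 15 of 15 at 70% is 0.70^15 = 0.005.

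For a smaller balanced Cohort 4 of 6:6 (an assumed size), the rule as written has probability 0.50^6, 0.70^6 and 0.90^6, or 0.016, 0.12 and 0.53. The count across arms (6 of 12, placebo 10%) gives 0.09, 0.30 and 0.71.

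**Step 4: criterion 2.** At an assumed 20% severe-emesis rate on HM15136, criterion 2 as written is met with probability 0.26 (3 of 9) against 0.004 (8 of 15). Criterion 4, two subjects with severe adverse events, is met with probability 0.83 among 15 active subjects if severe emesis is graded as a severe adverse event. Criterion 2 therefore seldom decides anything on its own.

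**The case against.** The strongest reply is that the denominator is unstated rather than wrong. An unblinded committee that ignores placebo events could equally compute the percentage among active subjects, which gives 5/9 and 8/15. Protocol 7.3 leaves DMC operations to a charter that is not among the documents. This is a possible reading, but both documents print the criteria in full, count cohorts with placebo everywhere else, and nowhere change the denominator. A charter that corrects the rule would not correct the text.

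Second, 15 of 15 may not be what convenes the DMC. Blinded staff can only count across arms, and the DMC meets when criteria seem to be met. That is fair, and it makes the trigger less extreme. Placebo still dilutes it in Cohort 4: 0.12 against 0.78 in a 9:3 cohort, at 70% active and 10% placebo.

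Third, the practical reach is narrow, and most of this stands:

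- Meeting a criterion calls a meeting, at which continued dosing is one option.
- Cohort 4 may be smaller than 30, so the 15-of-15 figures are the extreme case, though the 6:6 figures still show a gap.
- In 9:3 cohorts criterion 2 is 3 subjects on either reading, and criterion 1 moves by only one.
- Cohorts 5–7 are capped at 0.06 mg/kg, Cohort 4's listed dose, so a missed trigger affects dosing within Cohort 4 rather than escalation above it.
- Criteria 4 and 6 use absolute counts and, with criterion 7, largely cover severe emesis.
- The gastrointestinal guidance in the protocol Appendix suggests holding treatment in individuals whose symptoms need medical intervention.

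Individual management does not replace a cohort-level signal, however, and DMC judgement outside the planned dose decisions helps only once the DMC has been called.

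**Conclusion.** The concern holds. Read literally, criterion 1 requires 67% of active subjects in a 9:3 cohort and 100% in a balanced Cohort 4, and criterion 2 requires 33% and 53%. Those figures follow exactly from the text and the planned cohort sizes. The trigger probabilities depend on assumed emesis rates and on who does the counting, but Cohort 4 comes out well below the 9:3 cohorts for criterion 1 at every rate examined, even with a blinded count across arms.

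The consequence is moderate. The gap that matters is moderate emesis lasting under 7 days in Cohort 4. This should be fixed because it sits in the protocol's main tolerability rule and the correction is cheap.

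**What to change.** In Protocol 7.3 and SAP 2.4, express both percentages as a share of the subjects receiving HM15136 in the cohort, and print the counts:

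- Criterion 1: 5 of 9 in 9:3 cohorts and 8 of 15 in Cohort 4.
- Criterion 2: 3 of 9 and 4 of 15.
- If Cohort 4 is smaller, recalculate from the number on active drug. With 6 active, the counts are 0.50 × 6 = 3 and 0.25 × 6 = 1.5, rounded up to 2.

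To preserve the blind, let blinded staff convene the DMC when the number of affected subjects across both arms reaches the same count. That total can never be below the active-arm count, so no active-only trigger is missed. The DMC then removes placebo events.

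The cost is a wording change, with no added subjects, visits or assays, and somewhat more frequent meetings. At assumed rates of 20% on active and 10% on placebo, the active-only form of criterion 1 is met with probability 0.02 (5 of 9) and 0.004 (8 of 15). Convening on the count across arms would happen with probability 0.04 (5 of 12) and 0.07 (8 of 30).

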8.1. Test Product

Product or Code Name:	HM15136
Manufacturer:	Hanmi Pharmaceutical Co., Ltd.
Formulation/Properties:	pre-filled syringe with a clear or almost colorless transparent sterile solution
Raw material/Quantity:	A synthetic conjugate of a glucagon analogue (GC15136) and a G4 Fc portion of human immunoglobulin (HMC001). The concentration is 10 mg/mL as a protein and the total amount is 0.52 mL.
Storage:	Shade storage at 2 - 8 °C refrigerated condition (Stable at room temperature for up to 12 hours)
Expiration date:	Up to 24 months from date of manufacture

8.2. Comparator

Product or Code Name:	Placebo
Manufacturer:	Hanmi Pharmaceutical Co., Ltd.
Formulation/Properties:	pre-filled syringe with a clear or almost colorless transparent sterile solution
Raw material/Quantity:	Including excipients excluding the main components of the test product
Storage:	Shade storage at 2 - 8 °C refrigerated condition
Expiration date:	Up to 24 months from date of manufacture

8.3. Dosage and Administration

Each administration group will receive either HM15136 or placebo by subcutaneous injection in the abdomen after at least 10 hours night fasting state via SC once a week for a total of 12 weeks. Injection sites will be rotated within the abdominal area at subsequent visits.

8.4. Drug Supply, Package, Labelling and Storage

The IP should be packaged in accordance with local legal requirement, and in accordance with FDA requirements and specific country regulatory requirements.

The sponsor should pack the IP so that it is not contaminated or deteriorated during transportation or storage, and that packages of the test product and comparator can be easily distinguished according to each batch. The packing unit should consider the number of days of each visit and visit window, and provide an extra IP in order to prevent discontinuation of IP.

All supplied IP should be stored in shade storage (ie, kept in a box until use) at 2 - 8 °C refrigerated condition in accordance with the manufacturer's guidance. HM15136 is stable at room temperature for up to 12 hours. Until delivery to the subject, the IP should be kept in a secure location with locks and accessible only to authorized personnel.

8.5. Manufacture, Prescription, Inventory Management and Disposal/Destruction

8.5.1. Manufacture

The IP is provided in pre-filled syringes. The dosage of the drug is based on the weight measured on the day before the administration (up to two decimal places). The volume to be injected is also determined by the dose

level. The concentration of HM15136 is 10 mg/mL. The determined injection volume is prepared into the administration syringe according to the instructions contained in the pharmacy manual.

Per COVID-19 modification, weight may be measured on day -2 instead of day -1, and this weight may be used for the calculation of the IP dose for the individual subject.

8.5.2. Release of IP

Releasing of IP used for this study should be done on a subject-by-subject basis by the investigator or staff in charge of this study, after confirmation of subject eligibility

8.5.3. Inventory Management and Record

The management pharmacist should keep and manage a record of the randomization number, the date of the prescription, the number being released, etc., and check the inventory and keep a record of the receipt, storage, release, and returning of IP.

Each IP administered is also recorded.

Clinical research associate (hereinafter, CRA) for monitoring would regularly review administrative records to verify the use of all IP. The investigator is responsible for maintaining an accurate record of the IP management during the full period of study. And IP and related products should not be used for purposes other than those specified in the protocol.

[figure not shown]
The CRU will destroy all used syringes of IP and placebo at the CRU by the end of the study.

At the end of the study, all remaining IP, including unused and partially used IP will be destroyed in a documented process after confirmation by the responsible CRA.

9. Clinical Trial Methods and Administration Plan

9.1. Overall Clinical Trial Method

- = Accumulated safety data of Cohort 1 or Cohort 2 will be reviewed by the Data Monitoring Committee before dosing or screening of next cohort, respectively.
- = Accumulated safety data obtained from Cohort 1, 2 and through the 9th subject's visit on Day 29 in Cohort 3 will be reviewed by the Data Monitoring Committee, and determine proceeding to Part 2.
- = At Data Review Meeting, accumulated safety data obtained from previous cohorts, and through the 9th subject's visit on Day 43 will be reviewed.

★ An additional data review meeting will be held after all of the 12 subjects in Cohort 5 have completed the final study visit (F/U Visit) on Day 113. Cohorts 6 and 7 are optional.

Dosage, Method, Period of Investigational product

The IP will be injected to the subject via SC administration in 3 dose cohorts in Part 1, and in up to 4 cohorts in part 2.

Planned cohorts are below.

Part	Cohorts	Number of Subjects	Treatment
Part 1	Cohort 1	N=9	HM15136 0.02 mg/kg
		N=3	Placebo
	Cohort 2	N=9	HM15136 0.04 mg/kg
		N=3	Placebo
	Cohort 3*	N=9	HM15136 ≤0.08 mg/kg
		N=3	Placebo
Part 2**	Cohort 4	N=15	HM15136 0.06 mg/kg
		N=15	Placebo
	Cohort 5	N=9	HM15136 ≤0.02 mg/kg
		N=3	Placebo
	Cohort 6	N=9	HM15136 ≤0.04 mg/kg
		N=3	Placebo
		N=9	HM15136 ≤0.06 mg/kg

	Cohort 7	N=3	Placebo
--	----------	-----	---------

* Dosage of Cohort 3 can be adjusted, but not be over the dosage presented in the table. The escalated dose should not be over twice than the dose of the previous cohort.

** In part 2, if necessary, after the review of the safety data obtained by the 9th subject's visit on Day29 of Cohort 3 in Part 1, cohort can proceed within the 0.06 mg/kg dose, which is the planned maximum dose.

A DMC will assess the safety and will make dosing and cohort escalation assessments and recommendations for the study progress of Part 2.

For cohorts 5-7, after the safety data obtained by the 9th subject on day 43 are reviewed by Sponsor, investigator and medical monitor, dose escalation may proceed. An additional DRM will be held after all subjects have completed the dosing for Cohort 5.

Each subject will receive either HM15136 or placebo in the morning of Day 1 in the abdomen, after at least 10 hours night fasting state, via SC injection. The subject should maintain fasting state for 4 hours after the injection. After 4 hours, a post-administration assessment is performed, and a standardized lunch is provided to the subject. Per COVID-19 modification, if standardized lunch is not available, subjects may be provided with a snack bag.

The administration period of IP is a total of 12 weeks at once a week. Dosing windows for in-house and outpatient visits will be provided in the Operations Manual.

